Psychosocial Functioning: The 80-item Inventory of Psychosocial Functioning (IPF; Marx et al., 2009), was developed among Veterans to assess level of functional impairment. The IPF includes self-report and behavioral indices that assess current psychosocial functioning across 7 domains. Domain scores are summed to yield a total score for psychosocial functioning.

PTSD Symptoms. The PTSD Checklist – Military Version (PCL-M; Weathers et al., 1993) is comprised of 17 items that correspond to the 17 DSM-IV (APA, 2000) symptoms of PTSD. The PCL-M provides an index of global PTSD symptom severity and will be administered throughout the study. The 20-item PCL-M for DSM-5 is being piloted (Weathers et al., 2012; National Center for PTSD) and will be incorporated upon its release.

Measures: Potential Covariates and Secondary Measures. Potential covariates will be included in an initial analytic model for Stage 2 if deemed necessary (e.g., not evenly stratified through randomization).

Non-Alcohol SUD Diagnoses and Use. Non-alcohol SUD and other Axis-I psychiatric disorders will be determined at baseline with the SCID-I (First et al., 1995), modified for DSM-5. TLFB interview procedures (see above; Sobell & Sobell, 1992) will be used to assess patterns of non-alcohol substance use.

Attention Deficit Hyperactivity Disorder. Conner's Adult ADHD Diagnostic Interview for DSM-IV (CAADID; Epstein et al., 2001) will be administered at baseline to specifically asses for ADHD.

Alcohol Dependence Severity. The 10-item Alcohol Use Disorder Identification Test (AUDIT; Saunders et al.,1993) will be administered at each visit to assess alcohol dependence and harmful and hazardous drinking. Prescription Medication Use: All prescription medications will be documented at baseline. Changes in prescription medication use and dose will be tracked using self-report and the VA electronic medical record.

Training adherence and performance. Number of hours completed and aggregated performance indices (i.e., training effort and dose) will be recorded directly from the computer programs each training week.

AUD and PTSD Treatment: Information on past and concurrent AUD and PTSD treatment will be gathered at each study visit using the Psychosocial Treatment Interview (PTI) (Steketee et al., 1997).

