Depression and Anxiety: General levels of depression and anxiety will be measured at baseline and each study week with the 64-item Inventory of Depression and Anxiety Symptoms (IDAS; Watson et al., 2007).

Table 2. Overview of assessments to be administered

Clinical Assessments and Procedures	Phone Screen	Screening Visit	Baseline Assessment	Each Study Week	Week 3	Week 6 Post- Training	3 or 6 Month Follow up
Inclusion/Exclusion							_
Study Explanation	Χ						
Demographic Information	Х	Χ					
SCID-I – AUD		Χ					
CAPS – PTSD Interview		Χ					
Cognitive Screening-Table 1*		Х					
WTAR – Premorbid IQ Proxy		Х					
MMSE – Dementia Screen		Х					
DoD Severe TBI Screen		Χ					
Outcomes							
(S1) Acceptability/Usability Measures and Testing			X (orientation)		Х	X	
(S1) Interviews and/or Moderated Focus Groups					X	X	
Neuropsych Assessment			X			Χ	Χ
TLFB – Alcohol Consumption			X	Χ		Χ	X
DUQLS; IPF - Functional			X			Χ	X
PCL – M – PTSD symptoms			X	Χ		Χ	X
Potential Covariates, Second	lary Meas	ures					
TLFB - non-alcohol sub use				Χ		Χ	Χ
SCID-I (Axis 1 disorders)			X				
CAADID – ADHD			X				
AUDIT – AUD Severity			X	Χ		Χ	X
Training Adherence				Χ			
IDAS – Depression/Anxiety			X	Χ		Χ	Χ
PTI - Past/Current Treatment	Χ		X	Χ		Χ	X
Prescription Medication	Χ		X	Χ		Χ	Χ
Other							
Collateral h	istory fron	n medical re	cord/outpatien	t SUD tr	eatmen	t team as r	necessary
Study Informed Consent		Χ					
Randomization Checklist			Х				
Training Check-in Meetings				Х			
Breath Alcohol Concentration		X	Χ	Х		Χ	Χ

2a.3.j. Planned Data Analysis.

Missing Data. All laboratory-based measures will be reviewed for completeness immediately following collection, prior to the participant's dismissal. Despite our intensive protocol to limit participant attrition, we do expect missing data over the course of this study (i.e., 30%) and have adjusted our recruiting sample accordingly. To minimize the impact of missing data from incomplete protocols, we will use model-based multiple imputation procedures appropriate for longitudinal research described by Schafer and Graham (2002) and conduct analyses to evaluate the sensitivity of the results to model assumptions (Little & Rubin, 1987).

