The normality and range of data distributions will be examined and appropriate data transformations will be made when necessary. The data will also be screened for violations of assumptions underlying the statistical tests described below and when necessary, models will appropriately account for factors that vary with time across the study (i.e., training adherence). To control for Type-1 error rates cognitive outcomes will be tested using a Global Cognition Score (see 2a.3.i. Measures). Through randomization, we anticipate that the groups will be comparable in terms of demographic characteristics, premorbid intelligence, cognitive impairment, Axis-1 disorders, treatment participation, prescription medication use, training adherence and AUD and PTSD symptom severity. If significant differences exist, as indicated by Chi Square and t-tests, we will statistically adjust for these effects via inclusion as covariates in the analyses. We will conduct both a per protocol analysis on subjects who complete a minimum of 30 hours of training, and an intent-to-treat analysis on all randomized subjects, and report any differences in retention rates between the two conditions. For all models, variation inflation factors and tolerance will be obtained to assess for collinearity concerns. To account for family wise error, alpha will be adjusted in all secondary and exploratory analyses.

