Stage 2, Aim 2 Hypotheses 1a - b. Participants who receive cognitive training as compared to those receiving a computer-game control training, will demonstrate at 6 month post-training follow-up: Aim 2 Hypothesis a (Primary): greater improvements in cognitive outcomes (Global Cognition Score); Hypothesis b (Secondary): reduced alcohol consumption (drinks per drinking day) and PTSD symptoms (PCL-M) and improved quality of life outcomes (DUQLS, IPF). In order to test these hypotheses, a series of 5 multiple linear regression tests will be conducted to assess the effect of condition on each primary outcome. Step 1 will include the baseline level of the primary outcome. Condition (intervention, control) will be entered on Step 2. Step 3 will include any necessary covariates (described above in *Planned Data Analyses*) to determine if effects still remain. From this model we will be able to estimate the covariate and baseline adjusted mean changes, and 95%CIs, in global cognition, alcohol use, PTSD and quality of life outcomes 6 months posttraining. Secondary analyses. Planned secondary analyses will mirror the above description for primary analyses. First, to follow-up the analysis with global cognitive functioning, we will explore the effects of cognitive training on targeted cognitive domains using individual Cognitive Domain Scores as outcomes. Second, although we expect gains observed in the cognitive training group to be sustained throughout the follow-up period (i.e., persistence of neuroplasticity based cognitive training benefits), we will determine whether the Global Cognition Score changed from post-training to follow-up. This statistical approach is more dismantled and therefore more specific, and offers several advantages over repeated measures ANCOVA.

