Stage 2, Aim 2a Exploratory Hypothesis. Changes in global cognition will be significantly associated with decreases in alcohol consumption, PTSD symptom severity and increases in quality of life outcomes. Change scores will be computed for the Global Cognition Score, average drinks per drinking day, the PCL-M and the DUQLS and IPF, by computing the difference between follow-up and baseline. Four Pearson correlations will be performed to test associations between composite index change scores for Global Cognition and the 4 recovery outcomes. Exploratory Mediation and Moderation. We will explore potential mediators (i.e., training adherence and performance) and moderators (i.e., AUD and PTSD severity; Alcohol Use) of the effects of training condition on cognitive outcomes. The MacArthur approach to moderation and mediation analysis (Kraemer et al., 2008) will be employed. These analyses are considered exploratory

because, although the study is powered to detect main effects, we will have power to detect only very strong interaction and mediating effects.

2a.3.k. Timeline for Primary and Secondary Research Activities (See Table 3).

Primary Research Activities. During the start-up phase (months 1-3) of the proposed work, we will coordinate recruitment procedures with the outpatient SUD treatment program, finalize and purchase assessment and training tools and train study personal in the study protocol. A recruitment goal of 4 eligible participants per month was chosen based on prior experiences of the mentorship team who agreed that the goal was realistic and sufficient to meet study objectives, and to allow adequate time to conduct follow-up assessments. Recruitment for Stage 1 will start month 4 and last for 5 months. The weekly and post-training assessments for Stage 1 will be completed in month 9 and 3 month follow-ups will be completed in month 12. We will reserve time during months 13 and 14 to incorporate feedback from Stage 1 to refine the protocol and optimize feasibility for Stage 2. Stage 2 recruitment will begin at month 15 and will last until approximately month 46-47. Therefore, including start-up and Stage 1, all data should be collected by the *middle of year 5*.

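### The covariate rule adjusts the treatment effect for training adherence, which is measured after randomisation and is named elsewhere as a mediator

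*Combined protocol and SAP*

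**What the plan says.** All references are to the combined protocol and SAP.

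- **Section 2a.3.j, covariate rule.** A list of factors expected to be comparable through randomisation ends with adherence and symptom severity, and the trigger for adjustment follows at once: "training adherence and AUD and PTSD symptom severity. If significant differences exist, as indicated by Chi Square and t-tests, we will statistically adjust". Adjustment means entry as a covariate.
- **Same section, a few lines earlier.** Where necessary, "models will appropriately account for factors that vary with time across the study (i.e., training adherence"). Adherence is the only factor named.
- **Section 2a.3.i, Potential Covariates and Secondary Measures.** "Number of hours completed and aggregated performance indices (i.e., training effort and dose) will be recorded directly from the computer programs each training week". In Table 2 the row "Training Adherence" is marked only in the weekly study column. Section 2a.3.g places randomisation before orientation and training.
- **Section 2a.3.j, Stage 2 Aim 2.** Step 1 enters the baseline outcome, Step 2 enters condition, and Step 3 enters any necessary covariates "to determine if effects still remain. From this model we will be able to estimate the covariate and baseline adjusted mean changes" with confidence intervals. This applies to the Global Cognition Score and to the four secondary outcomes.
- **Section 2a.3.j, Exploratory Mediation and Moderation.** "We will explore potential mediators (i.e., training adherence and performance") of the effect of condition on cognitive outcomes.
- **Treatment participation and prescription medication** are in the same covariate list, but they have baseline as well as on-study values: "Information on past and concurrent AUD and PTSD treatment will be gathered at each study visit", and "All prescription medications will be documented at baseline" with later changes tracked.

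**The concern.** Randomisation balances what exists before assignment. Hours spent on BrainHQ or on Sporcle games come after assignment and may depend on which program the participant was given. A significant difference in adherence is therefore not a chance imbalance to correct; it may be an effect of the assignment. The plan accepts this possibility when it lists adherence as a mediator.

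Two errors can follow if adherence enters the effect model. If training works partly because people in that arm do more of it, adjustment removes that part of the effect. If training does nothing but adherence is related to outcome within each arm (through motivation, for example), adjustment creates a difference: a false benefit if the training arm adheres less, a false harm if it adheres more.

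The trigger makes this worse. It fires only when the arms differ in adherence, which is when adjusting for adherence can mislead. Step 2 and Step 3 may then disagree on the primary outcome, and the plan does not say which one counts.

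**Working it through.** **The plan's own figure.** Section 2a.3.j gives 80% power with 90 completers (45 per arm), d = 0.60 and two-sided alpha 0.05. Noncentrality is 0.60 × √(45/2) = 2.85 on 88 df, which gives 80.4%. The attrition arithmetic also agrees: 128 × 0.70 = 89.6. The stated power is reproduced, for an analysis without adherence in the model.

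**When the rule fires.** A t-test with 45 per arm reaches p < 0.05 when the observed adherence gap is at least 1.987 × √(2/45) = 0.42 SD.

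**Bias formula.** Let τ be the total effect, a the true adherence gap (training minus control, in within-arm SD) and s the slope of outcome on adherence within arms.

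- Adherence always in the model: expected estimate = τ − s·a.
- Adherence in the model only when significant: expected estimate = τ − s·E[D; rule fires], where D is the observed gap, approximately normal with mean a and SD √(2/45) = 0.211.

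For a = 0.5, the threshold lies at z = (0.419 − 0.5)/0.211 = −0.38, so P(fires) = 0.65 and E[D; fires] = 0.5 × 0.65 + 0.211 × 0.371 = 0.40. For a = 0.8 and a = 0.2 the same expression gives 0.79 and 0.08.

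**Assumed inputs (not in the documents).** Baseline–follow-up correlation of the outcome 0.6. Slope 0.3 when there is no true effect and 0.4 when there is one, multiplied by √(1 − 0.6²) = 0.8 to give 0.24 and 0.32 in the baseline-adjusted model. Slope equal in both arms.

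- a = 0.5, no true effect: bias 0.24 × 0.40 = 0.10 SD.
- a = 0.5, true effect 0.60: 0.60 − 0.32 × 0.40 = 0.47.
- a = 0.8, true effect 0.60: 0.60 − 0.32 × 0.79 = 0.35.

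**Simulation** (10,000 trials per scenario, 45 per arm, least squares, adherence added when its t-test gives p < 0.05). Baseline outcome in the model, as the plan specifies:

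| Adherence gap | Rule fires | No true effect: bias (absolute) | No true effect: type I error | True 0.60: estimate | True 0.60: power, Step 3 v Step 2 |
|---|---|---|---|---|---|
| 0.2 SD | 16% | 0.02 | 5% | 0.575 | 93% v 94% |
| 0.5 SD | 65% | 0.10 | 9% | 0.47 | 80% v 94% |
| 0.8 SD | 96% | 0.19 | 18–19% | 0.35 | 53% v 94% |

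Without the baseline term (the basis of the plan's own power calculation), a 0.5 SD gap gives bias 0.12 and type I error 9%; a true 0.60 is estimated at 0.44, with power 56% v 81%. At 0.2 SD the estimate is 0.57 and power 77% v 81%.

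**Sensitivity to the slope** (no baseline term, gap 0.5 SD, within-arm correlation 0.2, 0.3 and 0.5): power falls from about 80% to 66%, 62% and 52%. Type I error rises to about 7%, 8–9% and 18%, in whichever direction the gap lies.

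**What the documents say about the gap.** Pilot #1 (section 2a.2) reports 32.79 (SD 5.98) hours for 2 training participants and 31.38 (SD 7.54) for 3 controls. Pooled SD = √[(1 × 5.98² + 2 × 7.54²)/3] = 7.06, and 1.41/7.06 = 0.20 SD. The standard error is 7.06 × √(1/2 + 1/3) = 6.44 hours. With t = 3.18 on 3 df, the 95% interval is 1.41 ± 20.5, or −19.1 to +21.9 hours.

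**The case against.** **An unaffected estimate is already planned.** Step 2 contains only baseline outcome and condition, and Step 3 can be read as a robustness check on it. An intent-to-treat analysis is also promised. Step 2 is indeed sound. But no sentence makes it decisive, Step 3 is the stated test of whether effects persist, and the adjusted estimates are described as covariate-adjusted. Section 2a.3.i even speaks of covariates in an initial model. Intent-to-treat settles who is analysed, not which covariates enter.

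**The available evidence points to the harmless case.** The pilot gap is 0.20 SD, and dose, payment per session and weekly check-ins are the same in both arms. This is fair, and nothing in the documents supports 0.5 or 0.8 SD. Five people cannot exclude such gaps either.

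**The power losses depend on an equal slope in both arms.** Section 2a.3.h does not expect the control games to affect cognition, so extra hours may help only in the training arm. With the slope confined to that arm (baseline-adjusted), a true 0.60 is estimated at about 0.53 at a 0.5 SD gap and 0.47 at 0.8 SD. Power is then 86–90% and 73–77%, depending on how the simulation is set up, against 94%. This stands: attenuation is roughly halved. It does not touch the no-effect case, where a common cause such as motivation is enough to give a slope in both arms.

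**At 0.5 SD the baseline-adjusted power still meets the 80% target.** Correct, but the estimate is still biased.

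**Conclusion.** The concern holds. The plan states a rule that can place a post-randomisation variable, which it elsewhere calls a possible mediator, in the model for the primary outcome, and it does not make the unaffected Step 2 estimate primary. That part rests on the text alone and is firm.

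The size of the harm is conditional. It needs an adherence gap between arms, a relation between adherence and outcome, and Step 3 being taken as the result. At the pilot's gap of 0.2 SD it is negligible. At 0.5 to 0.8 SD, under the assumptions above, type I error is about 9% to 19% and a true 0.60 is estimated at 0.47 to 0.35; the loss is smaller if adherence matters only in the training arm. The Stage 2 gap is unknown.

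For treatment participation and prescription medication the fault is only ambiguity: the plan does not say whether baseline or on-study values would be used. The point should be fixed, but it does not undermine the design.

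**What to change.** 1. Delete training adherence from the covariate rule in section 2a.3.j. For the effect models, delete it also from the sentence on time-varying factors. Keep it for the exploratory mediation analysis.
2. State that treatment participation and prescription medication, if used as covariates, are baseline values.
3. Name the primary model: baseline outcome plus condition (Step 2), or that model plus baseline covariates fixed before unblinding.

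Fixing the covariates in advance would replace selection by chi-square or t-test. That is a secondary improvement on which this point does not depend, and the choice of any baseline covariates is the sponsor's.

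The cost is analysis-plan wording only: no new data, visits or participants. Without adherence in the model, the design keeps about 80% power at d = 0.60 on the plan's own calculation, and about 5% type I error.

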D1492-W at RR&D (Palo Alto) 6-1-2014 Cognitive Remediation for Alcohol Use Disorder and Posttraumatic Stress Disorder NCT02929979

2a. Research Plan

2a.1. Background and Significance

AUD, PTSD and Their Co-occurrence: Relevance to VA and to Treatment

Approximately one third of individuals seeking SUD treatment have PTSD (Ouimette & Brown, 2003) and compared to civilians, the prevalence of SUD and co-occurring PTSD is elevated among Veterans (Carter et al., 2011; Seal et al., 2011). Alcohol is the most common substance of abuse among patients with PTSD, and AUD is the most prevalent and costly SUD among Veterans (CESAR, 2012; SAMSHA, 2012). In fact, as many as 63-76% of OEF/OIF Veterans with an AUD have a co-occurring PTSD diagnosis (Seal et al., 2011). A wealth of research suggests that these disorders are intimately and functionally connected and thus highlights the importance of integrated care (Jacobsen et al., 2001; Schaefer & Najavits, 2007). Unfortunately, despite availability of empirically-supported treatments (EST) for co-occurring SUD and PTSD (Najavits & Hien, 2013), rates of relapse and non-response indicate an urgent need to improve recovery outcomes for this growing and highly vulnerable population.

Compared to individuals experiencing AUD or PTSD in isolation, co-occurrence of the disorders is associated with heightened risk for a host of negative outcomes. Among them include greater PTSD symptom severity, worse occupational, psychosocial and health outcomes, lower reported quality of life, increased interpersonal problems, higher rates of hospitalization and service utilization and increased risk of suicide and mortality (Carter et al., 2011; McCarthy & Petrakis, 2010;Schaefer & Najavits, 2007). In addition, PTSD is a robust predictor of poor SUD treatment response and relapse to drinking (Bradizza et al., 2006; Ouimette & Brown, 2003; Schaefer & Najavits, 2007). Collectively these studies demonstrate that AUD/PTSD patients have poorer clinical and functional outcomes and require more resources to treat than uni-morbid patients (McCarthy & Petrakis, 2010). Accordingly, this population of Veterans represents a critical target for increased attention as they are particularly susceptible to chronic impairment.

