The proposed research is a 2-stage prospective longitudinal investigation. It will investigate the impact of a tailored neuroscience-based cognitive training program (BrainHQ) on cognitive functioning and clinical and functional outcomes among Veterans with AUD and co-occurring PTSD, recruited from an outpatient SUD treatment program. The iterative design is based on guidelines put forth by the Stage Model of Behavioral Therapies per the National Institute on Drug Abuse (Carroll & Onken, 2005; Rounsaville et al., 2001). In both stages. Veterans will be randomized to receive either a computerized cognitive training or a computer-game control. Stage 1 ("Stage1a feasibility") will recruit 20 Veterans to examine and improve acceptability of both conditions and test and improve the usability of the computerized cognitive training program. The aim of Stage 1 is to inform efforts to maximize feasibility for Stage 2. In Stage 2 ("Stage 1b efficacy"), 128 Veterans will be recruited (Stage 1+2 recruitment = 148). The aim of Stage 2 is to examine the efficacy of cognitive training, as compared to a control condition, for improving cognitive functioning as well as alcohol, PTSD, and quality of life outcomes. Participants will complete 30 hours of web-based computerized cognitive training or computer games over 6 weeks, at a rate of 5 hours per week. In both stages, participants will complete a clinical and neuropsychological assessment battery at intake (baseline assessment), immediately following six weeks of training (post-training assessment), and 6-months post-training (follow-up; Stage 1 follow up is 3 months). In addition, in each week of the training period, participants will complete assessments (e.g., alcohol and substance use, mood) and check-in with research staff on their engagement in the training.

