During the screening assessment, participants will provide written informed consent. Next, a more detailed assessment of inclusionary/exclusionary criteria will be conducted (see section 2a.3e. Measures) and participants will be compensated \$30 for completion of this screening assessment. Individuals not meeting inclusionary criteria will be excluded from the remainder of the study. Individuals meeting all criteria will be scheduled to return for a baseline assessment. More specifically, participants will be administered structured clinical interviews, self-report questionnaires and remaining neuropsychological assessments, to collect baseline levels of responding. Participants completing the baseline assessment will be compensated \$50. Participants will be randomized in a 1:1 ratio to condition (training or control) and a checklist will be used to ensure that all study criteria are met before randomizing a participant. Participants will return to the lab the next business day for orientation to cognitive training (or computer game control) procedures and will be issued a loaned computing device (for descriptions of training schedule and platform delivery see section 2a.3.h. Method Overview). Participants will be compensated 10\$ for completion of the orientation session. Over the course of 6-weeks, participants will complete 30 hours of home-based cognitive training or computer games at the rate of 5 hours a week. Participants will earn \$5 for each completed training session (up to \$25 a week; \$150 total). Participants will be asked to refrain from alcohol or other substance use at least 4 hours prior to and during completion of training exercises. They will be advised that it is best to work on the programs in a quiet, preferably private location. Participants will log-in to a web-based cognitive training program or gaming site using a number assigned to their loaned wireless equipped computing device. Participant's engagement (i.e., adherence) and performance data will be sent to a secure server (i.e., no participant identifiers or personal health information); the data uploaded on the server will be identified only by the participant's assigned device number. A de-identifier sheet linking the device number to participant will be locked in the lab with access limited to study staff (See "Human Subjects" for specific details regarding the data security protocol). Participants will return to the lab at the end of each training week (i.e., 5 visits) to complete selfreport measures and participate in check-ins with the study coordinator regarding their level of engagement in the protocol. Participants will be compensated \$10 each study week they complete their lab-based session.

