Basic Attention and	Trail Making Test Part A*	Visuomotor Attention and Processing
Cognitive Bias	WAIS-IV Symbol Search	Speed
	WAIS-IV Digit Symbol	
	Approach-Avoidance Task	Attentional and Cognitive Biases

Verbal and Visual	Brief Visual Memory Test-R	Visuospatial learning and recall memory
Learning & Memory	Hopkins Verbal Learning Test–R*	Auditory learning and recall memory
Working Memory	WAIS-IV Arithmetic	Abstract Reasoning, Mental Calculation
	WAIV-IV Digit Span	Mental Tracking, Organization, Sequencing
	WAIS-IV Letter Numb Sequencing*	Mental Reorganization; Sequencing
Impulsivity and	Delis-Kaplan Color-Word Stroop Test	Inhibition of an over-learned response
Decision Making	Continuous Performance Task*	Sustained Attention, Vigilance, Inhibition
	Iowa Gambling Task	Decision-Making, Risk-taking
	Delay Discounting Task	Decision-Making, Reward Processing
Mental Flexibility	Wisconsin Card Sorting Task	Rule-Learning, Set-Shifting
	Delis-Kaplan Tower Task	Planning, Rule-Learning
	Trail Making Test Part B*	Speeded Set-Shifting

Measures: Alcohol Use

Alcohol Use. The Time-Line Follow-Back (TLFB) interview provides a calendar-guide of a targeted time period to help participants retrospectively record the number of standard drinks consumed on each day. The TLFB procedure has demonstrated good reliability and validity in past work across diverse samples (Sobell & Sobell, 1992) and data will be used to calculate the primary drinking outcome variable, average drinks per drinking day (the number of drinks consumed divided by the number of drinking days). The TLFB will be administered in an interview format at each study visit.

Breath Alcohol Concentration (BrAC). The *Intoximeter Alco-Sensor IV* (Intoximeters Inc.) instrument will be used to measure BrAC at each visit to ensure that subjects are not acutely intoxicated.

Measures: Functional Status and PTSD Symptom Severity.

Drug User Quality of Life Scale (DUQLS; Brogly et al., 2003). The DUQLS is a culturally relevant tool for assessing quality of life and satisfaction among individuals with SUD. Participants are also asked to classify each of the 22 life areas (including SUD treatment) as "important" or "unimportant" to them. Reponses on the DUQLS can be summed to generate an overall quality of life score as well as sub-scores that reflect quality of life in life areas that are important and unimportant to the participant.

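### Drinking, PTSD symptoms and mood are measured every training week, but no between-arm comparison of them is pre-specified before the 6-month follow-up

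*Combined protocol and SAP*

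**What the plan says.** **Collection.** The Design Framework in section 2a.3 states that "in each week of the training period, participants will complete assessments (e.g., alcohol and substance use, mood" among the examples. Section 2a.3.g gives the schedule: "Participants will return to the lab at the end of each training week (i.e., 5 visits", followed by the post-training assessment at week 6. Section 2a.3.i says of drinking that "The TLFB will be administered in an interview format at each study visit", and of PTSD symptoms that "The PCL-M provides an index of global PTSD symptom severity and will be administered throughout the study". On mood it says "General levels of depression and anxiety will be measured at baseline and each study week with the 64-item Inventory of Depression and Anxiety Symptoms". Table 2 marks TLFB alcohol, PCL-M, IDAS and AUDIT at baseline, each study week, week 6 and follow-up, and lists TLFB alcohol and PCL-M under outcomes.

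**Analysis.** In section 2a.3.j, Stage 2 Aim 2, the between-arm regressions for drinks per drinking day, PCL-M, DUQLS and IPF are set at the 6-month post-training follow-up. The reported estimates come from there: "From this model we will be able to estimate the covariate and baseline adjusted mean changes, and 95%CIs, in global cognition, alcohol use, PTSD", plus the DUQLS and IPF. The two named secondary analyses are both cognitive: domain scores, and change in the Global Cognition Score from post-training to follow-up. The exploratory correlations use follow-up minus baseline. Mediation and moderation concern effects on cognitive outcomes.

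**Covariates.** IDAS and AUDIT sit in section 2a.3.i under potential covariates and secondary measures, with the rule "Potential covariates will be included in an initial analytic model for Stage 2 if deemed necessary (e.g., not evenly stratified through randomization". Section 2a.3.j includes training adherence, which arises after randomisation, among the factors to be adjusted for if the arms differ.

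**The concern.** Section 2a.1 describes a population at raised risk of relapse, severe PTSD symptoms and suicide, and states that "PTSD is a robust predictor of poor SUD treatment response and relapse to drinking". The weekly TLFB, PCL-M and IDAS scores are the data that would show whether drinking, PTSD symptoms or mood moved in either direction while the training was in use. The planned clinical comparison comes about 7.5 months after randomisation (6 weeks of training plus 6 months). A worsening confined to the training period could be over by then, and no planned table or model would show it.

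A smaller matter is that the covariate rule is not limited to baseline values. Adjusting the arm comparison for something the intervention may have changed can remove part of its effect.

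**Working it through.** **1. The plan's own figure.** Section 2a.3.j states 80% power for d = 0.60 with 90 analysed (45 per arm), two-sided alpha 0.05. The noncentral t calculation gives 80.4%; the normal approximation gives 81.2%. Attrition: 128 × 0.70 = 89.6, and 128 − 90 = 38 (29.7%). The figures reproduce. The point does not depend on them, but they supply the group sizes used below.

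**2. Measurements against planned comparisons.** On-training time points: 5 weekly visits + week 6 = 6.
- TLFB, PCL-M and IDAS: 3 × 6 = 18 measurement occasions. DUQLS and IPF at week 6 add 2, making 20.
- Planned between-arm comparisons at these 20 occasions: 0.
- Planned between-arm comparisons of clinical outcomes at 6 months: 4 (drinks per drinking day, PCL-M, DUQLS, IPF).
- Planned comparisons of IDAS at any time: 0.

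**3. Precision available from data already collected.** Work in SD units of a single score. Let a be the correlation between any two on-training scores and b the correlation between baseline and each of them. The documents give neither; 0.5 to 0.8 is assumed for both, with b no larger than a. The variance of a participant's mean over six scores, after adjusting for baseline, is

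V = a + (1 − a)/6 − b²

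and the 95% CI half-width for the arm difference is 1.96 × √(2V/n), with n per arm. Power is the normal approximation for a 0.3 SD difference, an illustrative size that the plan does not name.

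| a | b | V | Half-width, n = 64 | Half-width, n = 45 | Power, n = 64 | Power, n = 45 |
|---|---|---|---|---|---|---|
| 0.8 | 0.8 | 0.193 | 0.15 | 0.18 | 97% | 90% |
| 0.5 | 0.5 | 0.333 | 0.20 | 0.24 | 84% | 69% |
| 0.8 | 0.5 | 0.583 | 0.26 | 0.32 | 60% | 46% |

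Example, last row: V = 0.8 + 0.2/6 − 0.25 = 0.583, and 1.96 × √(2 × 0.583/64) = 0.26. A baseline correlation well above the week-to-week one is not feasible at the extreme: a = 0.5 with b = 0.8 gives V = 0.583 − 0.64, which is negative.

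These figures assume all six scores from everyone and a difference sustained over all six weeks. A 0.3 SD worsening lasting two weeks averages to 0.3 × 2/6 = 0.1 SD, which is a reason to keep the arm-by-week term.

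**4. The drinking measure.** Section 2a.3.i defines the outcome as drinks divided by drinking days. In an abstinent week the divisor is zero, so it cannot serve as a weekly outcome. The SD-unit figures suit PCL-M and IDAS better than weekly drinking, which may be skewed.

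**The case against.** The strongest reply is that the stated hypothesis concerns 6 months, no adverse effect of the training is documented, and the missing table invalidates no planned inference. That stands, and it limits the weight of the point. Four stronger readings are tempting, and the documents support none of them.

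- **Harm would go unreported.** Section 2a.3.e refers to a Human Subjects section for the safety protocol, and that section is not in the supplied text. Nothing forbids reporting. What can be said is that no between-arm analysis is pre-specified.
- **Early leavers drop out of every clinical comparison.** Section 2a.3.j plans longitudinal multiple imputation with sensitivity analyses, an intent-to-treat analysis of all randomised participants, and a report of retention differences. Leavers may therefore enter the 6-month comparison, and the imputation variables are not listed, so weekly scores may inform it. The target is still the 6-month value, and a retention rate does not show who left after worsening.
- **A rise in IDAS will be adjusted away.** Nothing says weekly IDAS will be a covariate. Its heading also calls it a secondary measure, the example in the covariate rule points to imbalance at randomisation, and condition enters at Step 2, before covariates at Step 3. What remains is that the rule does not exclude post-randomisation values, training adherence is listed, and the reported mean changes are described as covariate-adjusted.
- **The plan claims training has no side effects.** The remark in section 2a.1 explains an advantage over medication. It is not a safety claim that the trial set out to test.

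**Conclusion.** The gap is real and rests on the text alone: 18 on-training occasions for TLFB, PCL-M and IDAS, no planned arm comparison at any of them, and no outcome analysis of IDAS at any time. A worsening during training that resolved by 6 months would appear in no planned result. The TLFB recall window at 6 months is undefined, but even a long average would tend to hide a transient rise.

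This is a worthwhile improvement to make before analysis; it does not undermine the planned 6-month inference. The data would give a useful, though not decisive, estimate: half-widths of about 0.15-0.26 SD at 64 per arm and 0.18-0.32 SD at 45 per arm, under the assumed correlations, complete weekly scores and a sustained difference. A reader who takes the two correlations as equal might infer power of 84-97% for 0.3 SD at 64 per arm. With 0.8 between weeks and 0.5 with baseline it is about 60%, so the analysis should be presented as estimation.

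**What to change.** 1. In section 2a.3.j, Stage 2 Aim 2, add an on-training estimation analysis of PCL-M, IDAS and TLFB alcohol use over weeks 1-6. Use a repeated-measures model with arm, week, arm by week and the baseline value, in all randomised participants with at least one post-baseline value. Report arm differences with 95% CIs, outside the alpha adjustment for secondary tests.
2. For weekly drinking, use a TLFB quantity that is defined in abstinent weeks, such as total drinks or number of drinking days.
3. Tabulate by arm the number worse than baseline, under a definition set in advance for analysis purposes, and the number who leave after worsening.
4. In sections 2a.3.i and 2a.3.j, limit adjustment covariates such as IDAS and AUDIT to their baseline values.

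The cost is a few sentences and one or two tables, with no new visits, measures or participants and no change to the planned sample size. The downside is a few extra estimates that are not multiplicity-controlled and need cautious reading.
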